## 1. Purpose of the Study and Background

The proposed study involves developing and testing a computer-assisted approach to delivery of screening and brief interventions, using a 'Substance Use Screening and Intervention Tool (SUSIT)' in primary care patients. Our central hypothesis is that introducing the SUSIT will facilitate the integration of substance use screening and interventions into primary medical care, resulting in higher rates of brief intervention by primary care providers and lower rates of unhealthy drug use in patients who receive the SUSIT intervention, as opposed to screening only. We propose to develop clinical decision support (CDS) and then test the full SUSIT model, incorporated into primary care medical visits. A mixed methods approach will assess its acceptability and adoption among providers and patients, and gather preliminary data on its efficacy for reducing 'moderate-risk' drug use (defined as unhealthy use that is below the threshold of a substance use disorder). In the main study period, a pre-post design will ascertain the dose of substance use intervention received and changes in drug use among patients with moderate-risk drug use enrolled in the screening only (SO) versus SUSIT intervention period (n=75 in each period).

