### 1.3. Study design

The proposed study will develop (in Phase 1) a clinical decision support tool that assists primary care providers in carrying out substance use interventions, and then compare (in Phase 2) two

PROTOCOL

s16-01074

[figure not shown]
clinical scenarios, screening only (SO) vs. SUSIT, on dose of substance use brief intervention

Version 8.6

01/22/2019

received, and changes in drug use at 3 and 6 months, among primary care patients. We will develop the CDS component and then test the full SUSIT approach, using mixed methods to assess its acceptability and adoption, and gathering preliminary data on its efficacy for reducing unhealthy drug use. CDS development is concurrent with the SO phase to avoid losing valuable time, but will be conducted at a secondary study site to avoid contaminating the SO condition. In each treatment condition we will enroll 75 patients with moderate-risk drug use, who present for a medical visit with one of ten PCPs (Figure 1). A pre-post design will ascertain the dose of substance use intervention received and changes in drug use among patients enrolled in the screening only (SO) versus SUSIT intervention period.

Figure 1: Study design

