## **2. Characteristics of the research population**

Main study sites: Bellevue Hospital Center (BHC) and Gouverneur Health will serve as the main study sites. Both sites serve a diverse and medically underserved population. The proposed study will recruit patients and primary care providers (PCPs) from the adult primary care clinics and the virology clinic at Bellevue Hospital Center. Up to 265 participants will be enrolled in the study. In Phase 1, up to 50 patients from Gouverneur Health and 35 PCPs from Bellevue and Gouverneur will participate in CDS development. In Phase 2, 150 patients and up to 30 PCPs from all study sites will participate.

Enrollment only sites: Two additional clinics are enrollment only sites, with limited study activities, in Phase 2 only. The enrollment only sites are two HIV clinics that function as primary care clinics. These sites are located at Lincoln Hospital in the Bronx, and Kings County Hospital in Brooklyn. Including these sites in the study offers an opportunity to understand the feasibility and impact of the SUSIT approach in a larger and more geographically diverse population of HIV primary care patients, but does not change the overall study aims or design. Enrollment only sites will have the same inclusion and exclusion criteria. The patients and PCPs from these sites are included in the overall limit (maximum 150 patients and 30 PCPs in Phase 2) for enrollment across all study sites.

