### 3.1.b. Phase 2: Screening Only (SO) vs. SUSIT

Phase 2 is conducted at Bellevue Hospital's Adult Primary Care Clinic and Virology Clinic. Adult patients of the participating PCPs will be recruited and enrolled following the procedures detailed in Section 5. The participating PCPs will receive screening results, CDS, and clinical reminders during the SUSIT condition, to help them address unhealthy drug use in their patients. The intervention that patients receive is determined by the period in which they are enrolled (i.e. Screening Only (SO)

vs. SUSIT), as indicated in Figure 3. Participating patients in both the SO and the SUSIT condition will enter responses to the tablet computer self-administered substance use screening tool. Screening is self-administered using a touch-screen tablet, and completed by patients in the waiting area prior to the clinical encounter. Substance use screening is part of a brief 'healthy lifestyle survey,' which also includes items on diet and exercise adapted from an existing health risk assessment. After the baseline medical encounter, patients will provide verbal responses to structured interviews. They will also complete a demographics form, and a self-administered computerized exit survey to ascertain whether their PCP provided elements of a substance use brief intervention during the medical visit, and various assessments described below. The exit survey will be administered again at any follow-up medical visits with the PCP that occur during the study period.

Figure 3. Study conditions

**Screening Only (SO) condition:** Patient and PCP are not presented with screening results. The PCP does not receive clinical decision support, or clinical reminders.

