**SUSIT condition:** Following completion of substance use screening, the tablet computer presents screening results (including level of risk) to the patient for each substance used, asks them to identify their drug of most concern (DOMC), and assesses readiness and confidence to change behavior. Results are delivered to the PCP at the point of care, paired with clinical decision support tailored to the patient's screening results. This information is delivered on the tablet computer, which is handed to the PCP by a Medical Assistant. CDS guides the PCP through a brief intervention specific to the DOMC, recommends clinical actions pertaining to the substance and risk level, and generates a printed summary for the patient. At each scheduled follow-up medical visit, the PCP receives a clinical reminder containing a summary of the patient's substance use and level of risk, paired with CDS that guides them through a follow-up brief intervention. A member of the study team will call, email, or text patients prior to these scheduled follow-up medical visits, to confirm that they will be attending.

**Phase 2 SUSIT Condition at Enrollment Only Sites:** Enrollment only sites will participate only in the Phase 2 SUSIT condition. All research activity at these sites is conducted by NYU Research Staff. The NYU research staff will obtain consent and enroll study participants (including both PCPs and patients), and only those individuals who give consent for participation will have any involvement with the study at these sites. After obtaining consent, the NYU research staff will conduct assessments

with enrolled patients at the baseline, 3 month, and 6 month study visits.

Patient participant assessments in SO and SUSIT conditions (Table 1)

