#### PCP assessments in Phase 2, SO and SUSIT conditions:

PCP focus groups: All participating PCPs will be invited to participate in focus groups, which occur prior to the SO period, and again 3 months following implementation of the SUSIT. Focus groups will be conducted by the PI to assess the provider-level factors that are anticipated to have the greatest impact on adoption. In the focus group conducted during the SUSIT period, themes will be explored in the context of their experience with the SUSIT.

Substance abuse attitudes survey: Provider attitudes can influence delivery of SBI to patients. Because PCPs may be reluctant to share negative attitudes toward substance use and users in a focus group, we will use the validated Substance Abuse Attitudes Survey (SAAS) to measure subjective norms. Because PCP attitudes may change in response to increased experience addressing substance use in their patients, the SAAS and modified TAM2 questionnaire will also be given at the end of the SUSIT period.

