#### Quantitative data analysis (Phase 2):

The data structure follows a hierarchy of patient-level data nested within providers, during the SO vs. SUSIT study period. For analysis of the primary outcome, which is measured at the patient level, we will first examine whether any brief intervention occurred, in at least one visit, during the study period. For additional descriptive information we will count the number of visits in which an intervention occurred, and the number of elements of the brief negotiated interview documented in each visit. The “receipt of brief intervention” outcome analyses will use a generalized linear mixed model (i.e., multilevel logistic regression) with a random intercept and patients nested within primary care providers. The key explanatory variable will be treatment condition (SUSIT vs. SO). When the fixed effect of treatment condition is exponentiated, this coefficient indicates how the odds of receiving brief intervention are multiplied when an individual receives the SUSIT condition rather than screening only. Patient-level and PCP-level covariates (e.g., substances used, provider SAAS score) can be added to the multilevel logistic regression analysis if they are significantly related to the odds of intervention. Any patient-level covariates will be grand mean centered following our focus on treatment condition effects.

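### Primary-model covariates are optional and chosen by significance with the outcome, with no fixed confounder set, in a comparison that is not randomised

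*Combined protocol and SAP*

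**What the plan says.** Section 3.2.a, Quantitative data analysis (Phase 2), is the only quantitative analysis text. The primary outcome is whether a patient received any brief intervention. The model is a multilevel logistic regression "with a random intercept and patients nested within primary care providers", and the only fixed effect it commits to is treatment condition. Other patient-level and PCP-level variables "can be added to the multilevel logistic regression analysis if they are significantly related to the odds of intervention". Substances used and the provider's SAAS score are given as examples, not as a list.

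The text gives no significance level and does not say whether a covariate is tested alone or with condition in the model. It requires no covariate, no check of differences between periods, and no adjustment for site or clinic type.

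Three other places bear on this:
- Section 3.1.b: "The intervention that patients receive is determined by the period in which they are enrolled".
- Section 3.1.b, on the two added clinics: "Enrollment only sites will participate only in the Phase 2 SUSIT condition". Section 2 describes them: "The enrollment only sites are two HIV clinics that function as primary care clinics".
- Section 3.1.b, PCP assessments: "the SAAS and modified TAM2 questionnaire will also be given at the end of the SUSIT period". Section 3.2.a does not say which SAAS score would enter the model.

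**The concern.** In a randomised trial, covariates mainly add precision. Here the two groups are recruited in different periods, so adjustment is the main protection against differences in patient mix. One difference is built in, because two HIV clinics supply SUSIT patients and no screening-only patients.

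A confounder is related to both period and outcome. The rule looks only at the outcome, and does so through a test with little power at 150 patients. A covariate that misses significance can still bias the SUSIT odds ratio. Because the wording is permissive, an unadjusted analysis also complies with the plan, and the choice could be made after the data are seen.

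The SAAS point needs clarifying. A score taken at the end of the SUSIT period may itself have been changed by SUSIT, so adjusting for it could remove part of the effect.

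**Working it through.** **Inputs.** From the documents: 75 patients per period (section 1), allocation by period, a logistic model, two SUSIT-only HIV clinics. The documents give no alpha, power, control rate, effect size, ICC or dropout, so the 75 per period cannot be reproduced. For context, 75 v 75 has 80% power (two-sided 0.05, clustering ignored) for 20% v about 41%, or 40% v about 63%. Every rate, imbalance and covariate effect below is an assumption. The true SUSIT odds ratio is 1, and the rule keeps a covariate if p<0.05.

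**Step 1. One binary confounder, unadjusted.** Let p0 be the event rate without the covariate, OR_c its odds ratio, and q0 and q1 its prevalence in SO and SUSIT. With p0 = 0.20 and OR_c = 2, the rate with the covariate is 0.5/1.5 = 0.333. For q0 = 0.2 and q1 = 0.5:
- SO rate = 0.20 × 0.8 + 0.333 × 0.2 = 0.227
- SUSIT rate = 0.20 × 0.5 + 0.333 × 0.5 = 0.267
- odds ratio = (0.267/0.733)/(0.227/0.773) = 1.24, with no true effect.

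**Step 2. The rule with one binary confounder.** Simulation, 2,000 runs per cell, no clustering, covariate tested with treatment in the model. Ranges cover p0 of 20% or 40% and prevalence of 20% v 50% or 30% v 70%. Unadjusted odds ratios are large-sample values; the others are medians.

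| OR_c | Kept by rule | Null OR: unadjusted / rule / always in | Type I error: unadjusted / rule / always in |
|---|---|---|---|
| 1.5 | 14-22% | 1.13-1.18 / 1.06-1.14 / 0.98-1.02 | 6.8-7.3 / 6.8-7.6 / 4.6-5.2% |
| 2 | 38-50% | 1.23-1.32 / 1.06-1.14 / 0.99-1.01 | 8.2-12.4 / 7.6-10.2 / 4.7-5.3% |
| 3 | 79-85% | 1.38-1.54 / 1.02-1.04 / 0.99-1.01 | 15.3-27.4 / 5.8-8.4 / 3.8-5.4% |

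The rule usually catches strong confounders and often misses moderate ones.

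**Step 3. Several modest confounders, all shifted the same way.** The unadjusted log odds ratio is roughly (number) × (shift in SD) × (log-odds per SD): 4 × 0.5 × 0.20 = 0.40, so OR about 1.49; 5 × 0.4 × 0.25 = 0.50, OR about 1.65; 4 × 0.3 × 0.20 = 0.24, OR about 1.27. Simulation gives 1.48, 1.62 and 1.27. Type I error at a 30% event rate, 4,000 runs per cell:

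| Covariates, shift, log-odds per SD | Unadjusted | Rule, tested alone | Rule, tested with treatment | All included |
|---|---|---|---|---|
| 4, 0.5 SD, 0.20 | 18.6% | 6.9% | 11.9% | 4.8% |
| 5, 0.4 SD, 0.25 | 25.6% | 7.6% | 13.1% | 5.0% |
| 4, 0.3 SD, 0.20 | 9.6% | 6.0% | 7.5% | 5.0% |
| 5, none, 0.25 | 5.1% | 5.3% | 5.9% | 5.3% |

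Over event rates of 30-50% with a shift, the rule keeps 19-37% of the confounders. The null odds ratio is 1.14-1.30, with type I error of 6.0-8.6% (tested alone) or 7.5-14.4% (with treatment). The full list gives 0.99-1.02 and 4.8-5.9%. At a 15% event rate the rule gives 1.17-1.38 and 5.3-10.9%.

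With a PCP random intercept (30 PCPs seeing patients in both periods, ICC 0.05, event rate 30%, 1,000 runs), the second row becomes 7.0 / 12.8 / 6.1% (alone / with treatment / all included), with odds ratios of 1.22 / 1.30 / 0.98. The third row becomes 6.5 / 7.6 / 5.0%, with 1.16 / 1.18 / 1.02.

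**Step 4. Clinic type as the only confounder.** HIV share 20-30% in SO v 50-60% in SUSIT, odds ratio 1.5-2, event rate 15-50%. The rule keeps it in 12-54% of trials. The null odds ratio is 1.05-1.10, with error of 4.1-5.3% (alone) or 5.9-7.1% (with treatment). Always included: 0.99-1.02 and 4.7-5.4%.

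**Step 5. SUSIT-only sites.** Suppose 15-35 of the 75 SUSIT patients come from the enrolment-only clinics and background odds there are 1.5-2 times higher (2,500 runs). Even with clinic type in the model the null odds ratio is 1.07-1.27 and type I error 5.0-9.3%. Restricting to sites with both periods gives 0.98-1.01 and 4.4-5.4%.

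**The case against.** The text is not in dispute; the size is. The strongest counter-arguments are these.

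- The larger figures need four or five confounders shifted in the same direction. The documents report no such imbalance, and eligibility criteria are the same at all sites. This stands: Step 3 shows what could happen, not what will.
- The imbalance the documents do support is clinic mix, and its effect is small. A mixed-model check with 20 Bellevue and 10 enrolment-only PCPs, 25 of 75 SUSIT patients from the latter, and 400 runs gave a null odds ratio of 1.06 under the rule, against 0.99-1.00 with clinic type always included, and no visible inflation of type I error. This also stands.
- Step 5 is mainly a design problem. The bias persists with clinic type in the model, so no covariate list cures it. Correct, which is why a restricted analysis is needed as well. The number of patients from those clinics is not given, so 15-35 is an assumption.
- The random-intercept runs in Step 3 have every PCP seeing patients in both periods. PCPs at enrolment-only sites cannot, and section 1.3 speaks of ten PCPs. True, but the runs without clustering show the same pattern.
- A fixed list has a cost, and the exact five variables are partly judgement. Both are true. The need for some pre-specified list does not depend on the exact choice.

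The rule is better than no adjustment. It remains weaker than a fixed list whenever the periods differ, and the permissive wording does not even guarantee that it is applied.

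**Conclusion.** The concern holds. Selecting covariates by their significance with the outcome, at the analyst's option, is the wrong rule for a comparison allocated by period. The harm depends on how far the periods differ: little or none without imbalance, a null odds ratio of about 1.05-1.10 if only clinic type differs, and up to 1.30 with type I error up to 14.4% at event rates of 30-50% if several modest confounders shift together. These sizes rest wholly on assumed inputs; the reading of the text does not. The plan should be changed, but this flaw alone does not invalidate the comparison.

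**What to change.** Replace the significance rule in section 3.2.a with five baseline covariates, included whatever their p-values:

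1. clinic type (adult primary care, or HIV, with Bellevue virology and both enrolment-only clinics in one category)
2. highest drug SSIS
3. number of substances
4. age
5. sex

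If fewer than 30 patients, pooled over periods, fall in the rarer outcome category, use only the first three. Report the unadjusted estimate beside the adjusted one. Add a sensitivity analysis restricted to sites that enrolled in both periods. If SAAS is used at all, use only a score taken before SUSIT exposure. State that adjustment does not remove secular trend or unmeasured confounding.

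**Cost.** SAP wording only; the variables come from the tablet screen, the demographics form and the site record. If all five were irrelevant (3,000 runs, true odds ratio 3, SO rate 15-30%), power would be 79% v 81% and 90% v 90%, with and without them. The estimate would be 3.16-3.20 instead of 3.04-3.08, about 4% further from the null (3.16/3.04 = 1.04), and type I error 4.7-4.9%.

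The fallback is needed because a 15% overall event rate gives 150 × 0.15 = 22.5 events over six slopes, about 4 each. It has limits: at 10%, 15 events over four slopes is again 3.75, so the SAP should also say how the adjusted estimate will be treated if events are that few. The both-period-site analysis is less precise (standard error 0.38-0.44 v 0.36-0.38).

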#### 3.2.b. Data monitoring

The PI will be responsible for reporting to the IRB and for monitoring all aspects of the study including adherence to the study protocol, quality assurance and adverse events. Monitoring of data quality will be conducted on an ongoing basis by the research team. Data on study enrollment and measures will be reviewed by the PI every 3 months.

While no study-related adverse events (AEs) are anticipated, any study-related adverse event that may occur will be recorded with the name of the event, the relationship to study participation, the severity and resolution. These reports will be reviewed by the PIs within 24 hours and reported to the IRB within 3 days of the adverse event's occurrence. These written reports will be stored in each subject's case file. The PI will review all study-related AEs reported during the previous month for the determination of seriousness, severity and relatedness, and will classify each AE as serious or non-serious. Study-related serious adverse events (SAEs) and unanticipated problems involving risks to participants or others (UAPs) related to study procedures will be reported to the IRB following NYU SoM reporting requirements. New information that may affect study participation will be provided to participants in a timely fashion. Study-related AEs and SAEs will be followed through resolution, stabilization or study end, and any serious and study-related AEs will be followed until resolution or stabilization, even beyond the end of the study. Subjects may be withdrawn from the study if continued participation would be harmful or for non-compliance with study procedures or for a serious adverse reaction to study procedures. The study may be discontinued on the recommendation of the PI or the NYU SoM IRB.

Data Safety and Monitoring Board (DSMB). A safety monitoring board will be established for ongoing protocol review, including data, protocol compliance, safety and efficacy data, in compliance with NIH and NYU guidelines. The DSMB is comprised of [name] (Chair), [name], MSc, and [name], MS.. All board members will meet NIH requirements regarding background and experience, and none will have ethical conflicts, including financial interest related to study outcome. Individuals invited to serve on the board will disclose any potential conflicts in writing. The board will meet every six months (unless more frequent meetings are deemed necessary). At each meeting, [name] and other research personnel will report on the trial status. This will be followed by a closed session under the direction of the DSMB chairperson, during which time the investigators and research team may be present. This will be followed by an executive session restricted to DSMB members. Issues discussed may include those related to subject safety and benefit, whether the primary study question is being answered, conflict of interest, confidentiality, and ongoing study review (including AEs, SAEs, and regulatory issues). Following each DSMB meeting, recommendations will be made by the chairperson to [name], and a final report (edited by all DSMB members) will be prepared and submitted to NIDA and the NYUMC IRB. Stopping the study due to safety concerns or interim analysis of the primary outcome are not anticipated.

### 3.3. Data storage and confidentiality

Data from the screening tool will be securely transferred to a database that resides on a HIPAA compliant cloud-based server; no data is stored on the tablet itself. The data will be backed up daily onto a password-protected secure storage drive. All computerized data (including substance use screening data, interviews, transcripts, audio recordings, screen recordings) is stored in a secure, double password-protected, storage drive that is maintained on a remote server by the NYU School of Medicine, and accessible only to members of the research team. Access to research offices at NYU is restricted to research staff, and the buildings where these offices are located are secure and monitored by security staff. File drawers containing participant information are located only at the NYU research office. These files are kept locked when not in use, and only research staff members have keys to these file cabinets. When the researchers are collecting data at the clinical sites, they will hand-carry a minimum amount of participant information required for that day's study visits on site, in a locked cabinet. At the end of each recruitment day, this information will be hand carried back to the research office and stored in a locked cabinet. Personal health information required to carry out the study (name, contact information, medical record number) will be stored separately from any study assessments. The only link between identifying information and the study ID will be kept in an electronic database, stored on a secure server under a separate password from that required to access the other study information.

Digital audio recordings and screen recordings will be uploaded within 24 hours in which the recording was made, to a password-protected secure storage drive on NYULMC Box. The recordings will be accessible only to members of the research team. Audio recordings will be sent for transcription within one week following the focus group or interview session, and only written transcripts will be used for analysis. Digital audio files will be deleted when data collection and transcription are completed, and video screen recordings will be deleted as soon as the usability testing analysis is completed.

